1 SYNOPSIS

Title: A Phase 2, Multicenter, Double-Blind, Parallel Group Long Term Extension Study in Rheumatoid Arthritis Subjects Who Have Completed a Preceding Phase 2 Randomized Controlled Trial with ABBV-105 Given Alone or in Combination with Upadacitinib (ABBV-599)	
Background and Rationale:	
This study will provide data on the long-term safety, tolerability, and efficacy of ABBV-105 and ABBV-599 in rheumatoid arthritis (RA) subjects who have completed the Phase 2 study of these compounds (Study M16-063). ABBV-105 is a novel, covalent Bruton's tyrosine kinase (Btk) inhibitor being developed for the treatment of immune-mediated inflammatory diseases including RA. ABBV-105 may be given alone or in combination with upadacitinib, which is known as ABBV-599. Upadacitinib is a novel Janus kinase (JAK) inhibitor, which displays unique selectivity for the JAK1 receptor.
 
ABBV-105 and ABBV-599 should be effective in decreasing signs and symptoms associated with active RA in patients with inadequate response or intolerance to biologic disease-modifying antirheumatic drugs (bDMARDs) by interfering with the JAK1/Btk pathways. Concurrent inhibition of JAK1/Btk pathways in RA may increase percent of those responding, as well as depth of response (relative to inhibiting either pathway alone), while maintaining an acceptable safety profile.
 
The clinical hypothesis for this study is that safety and efficacy of ABBV-105 and ABBV-599 will be maintained over an extended period of treatment.

Objective(s) and Endpoint(s):	
The primary objective of this study is to evaluate the long-term safety, tolerability, and efficacy of ABBV-105 and ABBV-599 in RA subjects who have completed Study M16-063.
 
Efficacy Endpoints
 
There is no primary endpoint since this is the extension to the feeder Study M16-063. Efficacy endpoints for this study, measured at each study visit, include the following:
 
 • Change in disease activity score (DAS)28 (C-reactive protein [CRP]) from baseline of Study M16-063; • Proportion of subjects achieving DAS Low Disease Activity (LDA), defined as DAS28 CRP \leq 3.2; • Proportion of subjects achieving DAS Clinical Remission (CR), defined as DAS28 CRP $<$ 2.6; • Change in clinical disease activity index (CDAI) from baseline of Study M16-063; • Proportion of subjects achieving LDA based on CDAI criteria, defined as CDAI \leq 10; • Proportion of subjects achieving CR based on CDAI criteria, defined as CR \leq 2.8; • Proportion of subjects achieving American College of

	
Rheumatology (ACR) 20/50/70 response;
 
 • Change in individual components of ACR from baseline of Study M16-063, to include swollen joint count (SJC), tender joint count (TJC), Patient's Assessment of Pain (using visual analog scale, VAS), Patient Global Assessment of Disease Activity (PtGA), Physician Global Assessment of Disease Activity (PhGA), Health Assessment Questionnaire Disability Index (HAQ-DI), and high-sensitivity C-reactive protein (hsCRP). • Change in Morning Stiffness from baseline of Study M16-063. 
Safety Endpoints
 
Safety evaluations include adverse event (AE) monitoring, physical examinations, vital sign measurements, electrocardiogram (ECG), and clinical laboratory testing (hematology, chemistry, and urinalysis) as a measure of safety and tolerability for the entire study duration.

Investigator(s):	Multi-center
Study Site(s):	The current assumption is to include approximately 39 sites in Canada and the European Union. Depending on operational aspects, the number, allocation, and location of sites may be modified.
Study Population and Number of Subjects to be Enrolled:	This long-term extension (LTE) study will enroll subjects who have completed Study M16-063. Only those subjects who have met all of the specified eligibility criteria will have an option to enter into the LTE study to receive continued therapy, provided the subject is willing and the investigator believes that continuing therapy is appropriate. Based on discontinuation criteria mandating efficacy, it is estimated that 20 - 60% of subjects (i.e., between 40 and 120 subjects) will ultimately complete the LTE.
Investigational Plan:	
This is a Phase 2, double-blind, multicenter, LTE study to assess the safety, tolerability, and efficacy of ABBV-105 and ABBV-599 in RA subjects who have completed Study M16-063. Subjects who meet eligibility criteria and enter the study on ABBV-105, ABBV-599, or upadacitinib from Study M16-063 will continue on their previously-assigned treatment through the end of the LTE study. Subjects who meet eligibility criteria and enter the study on placebo for both ABBV-105 and upadacitinib from Study M16-063 will receive ABBV-599.
 
The duration of the LTE study will be approximately 52 weeks. This includes a 48-week double-blind treatment period with study visits conducted at Weeks 18, 24, 30, 36, 48, and 60 from the baseline visit of Study M16-063. In addition, subjects will also have a telephone follow-up call 30 days after their last visit to determine the status of any ongoing AEs/serious adverse events (SAEs) or the occurrence of any new AEs/SAEs.

Key Eligibility Criteria:	Eligible subjects will have completed Study M16-063 (i.e., the preceding study of ABBV-105 and ABBV-599) and will have not developed any laboratory or clinical discontinuation criteria as defined in that study. Subjects must also not be currently enrolled or planning to enroll in any other interventional clinical study and must not require

	vaccination with any live vaccine during study participation (including at least 30 days after the last dose of study drug). Additional eligibility criteria are listed in the protocol Section 5.1.
Study Drug and Duration of Treatment:	
Study drug treatment assignments include the following:
 
 • Group 1: ABBV-599 (ABBV-105 60 mg and upadacitinib 15 mg) administered once a day (QD), • Group 2: ABBV-105 60 mg and upadacitinib placebo QD, • Group 3: ABBV-105 20 mg and upadacitinib placebo QD • Group 4: ABBV-105 5 mg and upadacitinib placebo QD, and • Group 5: Upadacitinib 15 mg and ABBV-105 placebo QD. 
At each visit where study drug is dispensed, each subject will receive 4 bottles of study drug; three of the bottles will contain capsules of ABBV-105 or matching placebo, and the remaining bottle will contain tablets of upadacitinib or matching placebo, all manufactured by AbbVie. Subjects will be instructed to take 1 capsule of ABBV-105 or placebo from each of the 3 dispensed bottles per day and 1 tablet of upadacitinib or placebo from the remaining dispensed bottle per day.
 
Study drug should be taken orally at approximately the same time each day, with or without food.

Date of Protocol Synopsis:	06 February 2020

2 INTRODUCTION

2.1 Background and Rationale

Why This Study Is Being Conducted

This study will provide data on the long-term safety, tolerability, and efficacy of ABBV-105 and ABBV-599 in rheumatoid arthritis (RA) subjects who have completed the Phase 2 study of these compounds (Study M16-063). ABBV-105 is a novel, covalent Bruton's tyrosine kinase (Btk) inhibitor being developed for the treatment of immune-mediated inflammatory diseases including RA. ABBV-105 may be given alone or in combination with upadacitinib, which is known as ABBV-599.

Btk is a non-receptor tyrosine kinase expressed in multiple immune cell types associated with the pathogenesis of RA and other autoimmune diseases. Btk is required for the propagation of pro-inflammatory signals downstream of immunoreceptors that promote autoimmune disease pathogenesis. Compared to other Btk inhibitors, such as CC-292 (Celgene) and ibrutinib (Pharmacyclics/Janssen), ABBV-105 showed better potency, superior selectivity, and less off-target activity, which is considered favorable for administration in humans.

Upadacitinib is a novel Janus kinase (JAK) inhibitor, which displays unique selectivity for the JAK1 receptor. Upadacitinib is currently being developed for the treatment of adult patients with moderately to severely active RA (Phase 3), psoriatic arthritis (Phase 3), atopic dermatitis (Phase 3), Crohn's disease (Phase 3), ulcerative colitis (Phase 2), axial spondyloarthritis (Phase 2), and giant cell arteritis (Phase 2). Development of other indications of interest (i.e., dermatomyositis and/or Takayasu arteritis) are under discussion. As of 20 June 2017, a total of 1232 subjects have received upadacitinib, which includes 469 healthy volunteers, 553 RA patients, and 210 Crohn's disease patients. Upadacitinib was generally well-tolerated, and the types of adverse events (AEs) seen were typical of patients treated with immunosuppressant therapies.

ABBV-105 given alone or as the ABBV-599 combination therapy (with upadacitinib) are anticipated to be effective in decreasing signs and symptoms associated with active RA in patients with inadequate response or intolerance to biologic disease-modifying antirheumatic drugs (bDMARDs) by interfering with the JAK1/Btk pathways. Concurrent inhibition of JAK1/Btk pathways in RA may increase percent of those responding, as well as depth of response (relative to inhibiting either pathway alone), while maintaining an acceptable safety profile.

Clinical Hypothesis

The safety and efficacy of ABBV-105 and ABBV-599 will be maintained over an extended period of treatment.

2.2 Benefits and Risks to Subjects

Preclinical toxicology studies of ABBV-105 in animals and ex vivo human samples suggest that the potential risks to human subjects of ABBV-105 are anemia, bleeding associated with platelet

dysfunction, and lymphopenia. Reductions in lymphocytes and the known mechanism of action suggest the potential for an increased susceptibility to infection.

ABBV-105 alone and the ABBV-599 combination therapy (with upadacitinib) were well-tolerated with no serious adverse events (SAEs) observed in healthy adult subjects at various doses in 3 Phase 1 studies (Studies M16-356, M16-357, and M16-044). The current study is a continuation of the Phase 2 study of ABBV-105 and ABBV-599 in RA (Study M16-063). Taken together, the safety data from the Phase 1 program and the safe and successful completion of Study M16-063 support further development of ABBV-105 and ABBV-599 in Phase 2 in subjects with RA.

The data from over 4,000 RA patients treated with upadacitinib support an acceptable safety profile and a positive risk-benefit for treatment of adult patients with moderately to severely active RA.

Data from the primary efficacy analyses of the 5 pivotal Phase 3 clinical studies for the upadacitinib RA development program consistently demonstrated the efficacy of upadacitinib 15 mg QD and 30 mg QD, with both doses of upadacitinib meeting all primary and ranked key secondary endpoints across all studies which included all lines of therapy (methotrexate [MTX]-naïve, conventional synthetic disease-modifying antirheumatic drug [csDMARD]/MTX-inadequate responder [IR], and biologic disease-modifying antirheumatic drug [bDMARD]-IR). Upadacitinib 15 mg QD also demonstrated superiority over adalimumab across a broad range of efficacy measures. Overall, the efficacy data in the RA development program provide substantial evidence to support the use of upadacitinib as monotherapy or in combination with MTX and/or csDMARDs for the treatment of adults with moderately to severely active RA.

Serious infections and herpes zoster are identified risks for upadacitinib therapy. The rates of serious infections and herpes zoster for upadacitinib therapy are within the range of other marketed JAK inhibitor products.

In regarding to the potential for malignancy, per upadacitinib Investigator's Brochure version 18.0:

Few malignancies were reported in the controlled portions of the upadacitinib Phase 2 and 3 clinical studies precluding any conclusions about rates between treatment groups. The interim rate of total malignancies excluding and including non-melanoma skin cancer (NMSC) on upadacitinib in the Phase 2 open label extension Study M13-538, which includes long-term treatment data, are both 0.7 E/100 PY. The malignancy types reported in the clinical program have been consistent with that anticipated in the study population including solid tumors such as breast, prostate and lung cancer, lymphoma, and NMSC. A number of subjects with malignancy had pre-existing risk factors for malignancy and/or prior history of treatment with other immunosuppressive therapy.

The malignancy rate is higher in the upadacitinib 30 mg group compared to the 15 mg treatment group; however, the difference in rates is related to more cases of NMSC and not other malignancy types.

For further details, please see findings from completed studies, including safety data, in the most recent ABBV-105 and upadacitinib Investigator's Brochures.

For safety monitoring, the following are included in the protocol:

- Subjects meeting discontinuation criteria as part of the M16-063 study will be excluded.

- If a subject develops a serious infection or opportunistic infection with study treatment, study drug should be interrupted, and appropriate treatment of the infection should be initiated.
- SAEs of infection will be reviewed on a real time basis and queried for additional information as clinically indicated.
- A supplemental herpes zoster form will be used to collect additional information for any herpes zoster infections.

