If any of the following AEs in [Table 3](#) are reported, the following supplemental report(s) must be completed.

Table 3. Adverse Events Requiring Supplemental Reports

Adverse Event	Supplemental Report
Cardiac events Myocardial infarction or unstable angina Heart failure Cerebral vascular accident and transient ischemic attack Cardiovascular procedures (SAE Supplemental Procedure eCRF)	MACE eCRF
Discontinuation or interruption of study drug due to a hepatic-related AE A hepatic-related SAE ALT/AST > 8 × ULN or ALT/AST > 3 × ULN with a total bilirubin > 2 × ULN	Hepatic AE eCRF
Renal impairment Renal dysfunction Renal failure Serum creatinine > 2.0 mg/dL	Renal eCRF
Herpes zoster infection	Herpes Zoster eCRF
Thrombotic events Non-cardiac, non-CNS embolic or thrombotic event (i.e., deep vein thrombosis or pulmonary embolism)	Embolic and Thrombotic (non-cardiac, non-CNS) eCRF

AE = adverse event; ALT = alanine aminotransferase; AST = aspartate aminotransferase; CNS = central nervous system; eCRF = electronic case report form; MACE = major adverse cardiovascular event; SAE = serious adverse event; ULN = upper limit of normal

If an AE meets any of the following criteria, it is to be reported to AbbVie or Contract Research Organization (as appropriate) as a SAE within 24 hours of the site being made aware of the SAE:

Death of Subject	An event that results in the death of a subject.
Life-Threatening	An event that, in the opinion of the investigator, would have resulted in immediate fatality if medical intervention had not been taken. This does not include an event that would have been fatal if it had occurred in a more severe form.
Hospitalization or Prolongation of Hospitalization	An event that results in an admission to the hospital for any length of time or prolongs the subject's hospital stay. This does not include an emergency room visit or admission to an outpatient facility.
Congenital Anomaly	An anomaly detected at or after birth, or any anomaly that results in fetal loss.

Persistent or Significant Disability/Incapacity

An event that results in a condition that substantially interferes with the activities of daily living of a study subject. Disability is not intended to include experiences of relatively minor medical significance such as headache, nausea, vomiting, diarrhea, influenza, and accidental trauma (e.g., sprained ankle).

Important Medical Event Requiring Medical or Surgical Intervention to Prevent Serious Outcome

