An important medical event that may not be immediately life-threatening or result in death or hospitalization, but based on medical judgment may jeopardize the subject and may require medical or surgical intervention to prevent any of the outcomes listed above (i.e., death of subject, life threatening, hospitalization, prolongation of hospitalization, congenital anomaly, or persistent or significant disability/incapacity). Additionally, any elective or spontaneous abortion or stillbirth is considered an important medical event. Examples of such events include allergic bronchospasm requiring intensive treatment in an emergency room or at home, blood dyscrasias or convulsions that do not result in inpatient hospitalization, or the development of drug dependency or drug abuse.

All AEs reported from the time of study drug administration until 30 days after discontinuation of study drug administration will be collected, whether solicited or spontaneously reported by the subject. In addition, SAEs and protocol-related nonserious AEs will be collected from the time the subject signs the study-specific informed consent.

AbbVie will be responsible for Suspected Unexpected Serious Adverse Reactions (SUSAR) reporting for the Investigational Medicinal Product (IMP) in accordance with global and local requirements.

AEs will be monitored throughout the study to identify any of special interest that may indicate a trend or risk to subjects.

Adverse Events of Special Interest

The following adverse events of special interest (AESI) will be monitored during the study:

- Serious infections
- Opportunistic infections
- Herpes zoster
- Tuberculosis
- Malignancy (all types)
- Gastrointestinal perforations
- Adjudicated cardiovascular events (e.g., major adverse cardiovascular event [MACE])
- Anemia
- Neutropenia

- Lymphopenia
- Increased serum creatinine and renal dysfunction
- Hepatic events and increased hepatic transaminases
- Elevated creatine phosphokinase
- Embolic and thrombotic events (non-cardiac, non-CNS)

Adverse Event Severity and Relationship to Study Drug

The investigator will rate the severity of each AE according to the Rheumatology Common Toxicity Criteria v.2.0. **If no grading criteria are provided for the reported event, then the event should be graded as follows:**

- Mild (Grade 1): Asymptomatic or mild symptoms; clinical or diagnostic observations only; intervention not indicated.

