### **9.2.2 Adverse Event Overview**

The number and percentage of subjects experiencing TEAEs will be summarized by treatment group as specified in Section 6.0 and overall.

An overview of AEs will be presented consisting of the number and percentage of subjects experiencing at least one event for each of the following AE categories:

- All TEAEs
- Treatment-emergent serious adverse events (SAEs)
- Treatment-emergent severe adverse events
- TEAEs reasonably possibly related to study drug
- TEAEs of special interest (AESIs)
- TEAEs leading to discontinuation of study drug

- TEAE leading to death
- All deaths

Additional AEs may be considered for tabulation/summary based on recommendations from Clinical and Safety as deemed appropriate.

For AESIs, the point estimate and 95% CI (using normal approximation) will be provided for the treatment difference in AE percentages.

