### **9.2.3 Treatment-Emergent Adverse Events by SOC and/or PT**

The number and percentage of subjects experiencing adverse events will be tabulated by SOC and MedDRA PT by "as treated" treatment groups and overall. The SOCs will be presented in alphabetical order, and the PTs will be presented in alphabetical order within each SOC.

The following summaries of adverse events will be generated:

- All TEAEs
- Treatment-emergent serious adverse events (SAEs)
- Treatment-emergent severe adverse events
- TEAEs reasonably possibly related to study drug
- TEAEs leading to discontinuation of study drug
- TEAE leading to death
- Frequent AEs (reported in 2% of subjects or more in any treatment group)

Subjects reporting more than one adverse event for a given MedDRA preferred term will be counted only once for that term (most severe incident for the severity tables and most related incident for the relationship tables). Subjects reporting more than one type of adverse event within a SOC will be counted only once for that SOC. Subjects reporting more than one type of adverse event will be counted only once in the overall total. In addition, if the same adverse event occurs multiple times within a subject, the highest

severity and level of relationship to investigational product will be reported. In addition, TEAEs will be summarized by PT and sorted by decreasing frequency for the total active group.

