## **11.0 Interim Analysis**

An interim analysis to review long-term safety and efficacy will be conducted after Study M16-063 Week 12 database lock and analysis. The descriptive statistics will be presented for key efficacy and safety endpoints with all available data at the interim analysis. Key efficacy endpoints include DAS28(CRP), CDAI, ACR20/50/70, Patient's Assessment of Pain [using visual analog scale, VAS], and HAQ-DI. Key safety endpoints include overview of TEAE, TEAEs reasonably possibly related to study drug, SAEs, TEAE leading to death, AESIs, mean change from baseline for hematology and chemistry, PCS for hematology and chemistry and liver-related elevations.

Unblinded interim analyses for safety will be conducted by a DMC to review safety. The sponsor, study sites and subjects will remain blinded for the duration of the study until the database lock of Study M16-063.

An internal data monitoring committee (DMC) will review unblinded safety data from the ongoing study. The primary responsibility of the DMC will be to protect the safety of the subjects participating in this study. A separate DMC charter has been prepared outside of the protocol and describes the roles and responsibilities of the DMC members, frequency of data reviews, relevant safety data to be assessed, and expectations for blinded communications.

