## Appendix B. Definition of Adverse Events of Special Interest

Adverse Events of Special Interest (AESI) will be identified using the following search criteria:

AESI	Type of MedDRA Query	Broad or Narrow Search	SMQ/CMQ Search Criteria
Serious Infections	CMQ		"Infections" – Subset for SAEs
Opportunistic Infection	CMQ		"Opportunistic Infection"
Possible Malignancy	SMQ	Narrow	"Malignancies"
Malignancy	SMQ		"Malignant tumours"
Non-Melanoma Skin Cancer (NMSC)	SMQ	Broad	Skin Malignant tumours (Broad SMQ) removing Melanoma CMQ
Malignancy excluding NMSC			"Malignant tumours" SMQ removing NMSC output
Lymphoma	SMQ		"Malignant Lymphomas"
Hepatic Disorder (Hepatic Events and Increased Hepatic Transaminases)	SMQ	Narrow	"Drug Related Hepatic Disorders"
Gastrointestinal Perforations	SMQ	Narrow	"Gastrointestinal Perforation"
Anemia	CMQ		"Non-Hemolytic and Non-Aplastic Anemias"
Neutropenia	CMQ		"Hematological Toxicity – Neutropenia"
Lymphopenia	CMQ		"Hematological Toxicity – Lymphopenia (Veliparib Product Specific)"
Herpes Zoster	CMQ		"Herpes Zoster"
Creatine Phosphokinase (CPK) Elevation	PT		Search only for the PT of "Blood creatine phosphokinase increased"
Renal Dysfunction	SMQ	Narrow	"Acute Renal, Failure"
Tuberculosis	CMQ		"Tuberculosis"
Adjudicated Cardiovascular Events	Output from CAC		

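### Bleeding is a potential ABBV-105 risk named in Protocol 2.2, but it is the only risk named there that is in neither AESI list, so no planned output pools bleeding terms and non-serious bleeding can be diluted across them

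*Protocol*

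**What the plan says.** Protocol 2.2, drawing on animal toxicology and ex vivo human samples, states that the "potential risks to human subjects of ABBV-105 are anemia, bleeding associated with platelet" dysfunction, and lymphopenia. The next sentence adds a possible increase in susceptibility to infection.

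Protocol 6.1 introduces its list with "The following adverse events of special interest (AESI) will be monitored during the study" and gives 14 categories. SAP Appendix B opens with "Adverse Events of Special Interest (AESI) will be identified using the following search criteria" and has 17 rows. Neither contains bleeding or haemorrhage. Protocol Table 3, "Adverse Events Requiring Supplemental Reports", has no bleeding form, and Protocol 6.2 has no bleeding paragraph.

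AESI status has consequences in the SAP:

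- Section 9.2.2: "For AESIs, the point estimate and 95% CI (using normal approximation) will be provided for the treatment difference in AE percentages".
- Section 9.2.6 gives a grouped AESI summary.
- Section 9.2.11 gives a subject listing.
- Section 11.0: "Key safety endpoints include overview of TEAE, TEAEs reasonably possibly related to study drug, SAEs, TEAE leading to death, AESIs".

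Protocol 7.4 also promises AESI percentages and event rates per 100 patient-years.

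**The concern.** Evaluating long-term safety is part of the primary objective, and the protocol itself says which harms of ABBV-105 it expects might occur. All but one were carried into the focused safety outputs, and neither document gives a reason for the exception.

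Bleeding also depends on pooling more than the other named risks do. Anemia and lymphopenia each have a laboratory measure, whereas bleeds at different sites are reported under different terms. Laboratory data help only indirectly. SAP Table C-1 grades platelet count, but the stated risk concerns platelet function. Haemoglobin decrease and haematuria capture only part of the picture.

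What is at stake is whether the trial can state, by a rule fixed in advance, how many subjects in each group bled.

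**Working it through.** **Step 1. Named risks against the two lists.**

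| Risk in Protocol 2.2 | Protocol 6.1 AESI list | SAP Appendix B |
|---|---|---|
| Anemia | yes | yes |
| Bleeding (platelet dysfunction) | **no** | **no** |
| Lymphopenia | yes | yes |
| Susceptibility to infection | yes (serious, opportunistic, herpes zoster, tuberculosis) | yes (the same four) |

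**Step 2. Where a bleed would appear as planned.**

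- *Any bleed:* the all-TEAE table by SOC and PT (SAP 9.2.3, no threshold), the severity and relationship tables (9.2.7, 9.2.8) and the general TEAE rates (9.2.4).
- *Serious, severe, related, fatal or treatment-stopping bleed:* also the corresponding tables (9.2.3, 9.2.5). SAEs, deaths and discontinuations are listed as well (9.2.11).
- *Non-serious bleed that does not stop treatment:* none of the 9.2.11 listings. If it is also judged unrelated, the AE outputs named for the interim count it only within the overview totals and do not itemise it.
- *Bleeding as a group:* no output.

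**Step 3. Group size (assumption).** The documents give no size per group. The completer estimate is 20-60%, or 40 to 120 subjects. It is consistent with one base: 40 / 0.20 = 200 and 120 / 0.60 = 200. Treating 200 as the number of entrants and splitting it equally over the six entry groups gives 200 / 6 = 33. I also use 20 and 40.

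**Step 4. Thresholds.** Section 9.2.3 includes "Frequent AEs (reported in 2% of subjects or more in any treatment group". One subject reaches 2% in any group of 50 or fewer (1/50 = 2.0%; 1/33 = 3.0%), so under these sizes every bleeding term would be shown there. Section 9.2.10 requires more than 5% in some arm. That takes 2 subjects with the same term at n = 20 (1/20 = 5.0%, not above) or n = 33 (2/33 = 6.1%), and 3 at n = 40 (2/40 = 5.0%, not above).

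**Step 5. Dilution.** Suppose 5 of 33 subjects bleed, each with a different term:

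- Pooled: 5/33 = 15.2% (Wilson 95% CI 6.7-30.9%).
- Per term: 1/33 = 3.0%. None enters the above-5% table unless the same term passes 5% in another arm.

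**Step 6. How often this happens in one arm.** Assume a true bleeding risk of 10%, five equally likely terms and one term per bleeding subject. The pooled probability is binomial. At n = 33 it is 1 - 0.9^33 - 33 × 0.1 × 0.9^32 = 1 - 0.031 - 0.113 = 0.86. The single-term probability comes from a multinomial simulation of 200,000 draws.

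| n per group | Count needed for >5% | P(pooled >5%) | P(at least one term >5%) |
|---|---|---|---|
| 20 | 2 | 0.61 | 0.27 |
| 33 | 2 | 0.86 | 0.54 |
| 40 | 3 | 0.78 | 0.21 |

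Varying the risk from 6% to 15% and the number of terms from 3 to 8 at these sizes, the pooled probability runs from 0.34 to 0.97 and the single-term probability from 0.03 to 0.88. The pooled figure is the larger in every combination.

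**The case against.** A reader might infer that a bleeding signal would be missed in every focused safety output. The documents do not support that. Step 2 shows that clinically important bleeds reach their own tables whatever their AESI status, and that related or serious bleeds are already among the interim endpoints. Only the above-5% table can omit a term under the assumed sizes, and even there some single term often passes.

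The illustration uses a bleeding rate, a number of terms, an even split and group sizes that the documents do not give. An even split is unfavourable to the plan. Pooling also leaves wide uncertainty. Section 9.2.2 names no reference arm for the AESI treatment difference, so the contrast bleeding would gain is no better defined than for existing AESIs. These points stand and limit the size of the finding.

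Neither document says that every potential risk must be an AESI. Section 2.2 bases this one on preclinical work and reports no SAEs in three Phase 1 studies in healthy adults. The omission is therefore a design choice, not a contradiction.

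SAP 9.2.2 also leaves a route open: "Additional AEs may be considered for tabulation/summary based on recommendations from Clinical and Safety as deemed appropriate". That route is discretionary. A grouping chosen after the unblinded interim in Protocol 7.5 is weaker evidence than one fixed beforehand, so the clause does not secure the summary.

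Table C-1 places petechiae, gastrointestinal bleeding and haematuria under different systems. It is a grading scale and not the coding dictionary, so it illustrates scatter without proving how terms will be coded.

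**Conclusion.** The point holds in a limited form. Of the ABBV-105 risks that Protocol 2.2 names, only bleeding is missing from both AESI lists. As a result, four things are not prespecified: a pooled incidence, an AESI subject listing, a between-group estimate, and a bleeding category in the interim AESI review. The exposed events are mainly non-serious bleeds spread over several terms.

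A size can only be illustrated: 15.2% pooled against 3.0% per term in an assumed group of 33, with the direction unchanged across the ranges tried. It would go too far to say that the long-term safety objective is left unanswered for bleeding, since every event is still collected and tabulated by term. The gap is the missing pooled summary.

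The AESI list and Appendix B are fully visible, so the omission is certain. Its practical effect is less so, because the Operations Manual text, the Investigator's Brochure and the DMC charter were not available and may provide for bleeding review.

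**What to change.** Treat this as a cheap improvement:

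1. Add bleeding events to the AESI list in Protocol 6.1.
2. Add a matching row to SAP Appendix B using a MedDRA haemorrhage query, with its type and scope stated as for the other rows. Show it overall and for serious or Grade 3 and higher events.
3. Change both documents together. A row added to the SAP alone would leave its AESI set different from the protocol's on this category.

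The category then carries into SAP 9.2.2, 9.2.6, 9.2.11 and 11.0 without further edits. To keep the benefit of prespecification, make the change before the unblinded interim data are reviewed.

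The cost is one protocol line and one SAP row, run on adverse events already collected and coded. No visit, form, dose or clinical rule changes. The downside is that minor bruising enters the pooled row, which the serious or Grade 3 and higher split addresses.
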